### **3.2.2 Bayesian causal inference Model Testing**

The statistical performance of models will then be assessed ‘out of sample’ on the remaining 20% of specimens in the same retrospective dataset. The techniques used to assess and refine the initial LR-derived model will be developed using R, Stan, and Python programming languages, and will consist of:

- Counterfactual analysis: Input variables will be sequentially removed from and returned to the model to ascertain their likely causative impact, and therefore determine whether they should be included in the final model(27). Where sufficient data are available, sensitivity analyses will also be performed to analyse to ensure that unjustified prediction inequalities do not occur(41).
- Scoring rule loss functions: Different performance assessments will be required depending on the models used. For LR, measures such as log loss score and AUC-ROC will provide measures of model accuracy by quantifying difference between the probability of antimicrobial susceptibility predicted by the model and observed antimicrobial susceptibility(55,56).

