Infection management has been of particular interest in the field of precision medicine because the threat of sepsis combined with the ongoing proliferation of antimicrobial resistance means that antibiotic therapy needs to be not only efficacious, but also prompt and targeted(19). Several studies have employed statistical techniques to predict antimicrobial susceptibility testing in UTI. Methods for these applications have included logistic regression (LR), decision trees, random forest models, neural networks, and extreme gradient boosting. The predictive performance of models versus eventual culture(s) and clinical outcomes are evaluated using metrics such as area under the curve receiver operating characteristic (AUC-ROC). The objective of these studies, however, has been very different to that of ADAPT-AST; this prior work has focused solely on clinical decision support for clinician antimicrobial treatment selection at the bedside without consideration of the role of the laboratory. No studies to date have used adaptive prediction techniques to help personalise AST(20–24).

The findings of previous attempts to predict antimicrobial susceptibility algorithmically have been promising. The value of a bedside clinical decision tool, however, is affected by what has been referred to as the ‘chasm’ between demonstrating algorithmic accuracy and clinical effectiveness. This is due to a range of factors, which can only be mitigated by deep a priori knowledge of the clinical subject matter; for example, predictions based on AMR datasets are particularly vulnerable to ‘concept shift’ of training datasets caused by changes in organism ecology and clinical laboratory processes over time(25). Prescriptively directing antimicrobial administration using predictive algorithms is also problematic in the clinical setting where there is inherent situational uncertainty and the impact of

giving the wrong drug can be very high(26). Existing studies with limited specialist clinical involvement also suffer from an inability to separate causation from prediction, a particularly key distinction in medical microbiology where the complex host-microbe dynamic means that causal inference is not always straightforward(27).

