## **2 PROJECT QUESTIONS/AIMS**

The aim of this project is to develop and evaluate adaptive informatics approaches to supporting better clinical decisions over laboratory antimicrobial susceptibility testing for UTI pathogens compared with current practice, and thereby examine the potential to improve patient outcomes, reduce AMR risks and reduce waste of laboratory resources. The project questions are as follows:

1. Can causal, explainable BCI approaches be used to develop/(re)validate (train/test) clinical prediction models for prediction of urine organism antimicrobial susceptibility using NHS care data?
2. Can the resulting ADAPT-AST adaptive, informatics-based (data-driven and system-wide) approach target AST for UTI better than existing approaches can, thereby improving timeliness of clinical decision making (reducing unnecessary AMR selection pressure) and saving resources through efficiency?

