- Admission/consultation/past diagnoses data: Resistant organism colonisation is more likely in patients who have been exposed to healthcare(38).
- Prescribing data: Previous antimicrobial exposure is one of the key routes to development of drug resistance through induction of organism-level molecular resistance mechanisms and population-level selection of resistant organisms. Data on non-antimicrobial drugs will also be collected as this may be a surrogate marker of contact with healthcare that influences AMR risk e.g., drugs for benign prostatic hypertrophy(39)
- Microbiology data: Previous colonisation with an antimicrobial resistant organism is a risk factor for subsequent infection with an antimicrobial resistant organism; susceptibility data for all types of patient specimen will therefore be analysed (with appropriate algorithmic weighting), not just urine specimens(40). Specimen type and location type will also provide important information about risk factors (e.g., catheter specimen of urine, urology clinic specimens).

Protected characteristics were also considered for inclusion to prevent unintentional algorithmic discrimination. Characteristics considered were those defined by UK law: pregnancy, marital status, race, sexual orientation, gender reassignment, disability, religion and nationality (41,42). Data on these characteristics will not be collected because: 1. There are no proven or plausible reasons why these characteristics should directly and significantly impact AMR risk; 2. protected characteristic data contained within the relevant systems is likely to be incomplete and unreliable; 3. some protected characteristics (e.g., race or nationality) may increase the risk of participant identification due to the rarity of some characteristic types in the Liverpool area.

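### Section 3.2.2 reads the removal and return of inputs as causal evidence and as the inclusion rule, but the step measures only predictive contribution and is placed on the evaluation specimens

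*Protocol*

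**What the plan says.** Section 3.2.2 sets out how the prediction models are tested. Performance is to be "assessed ‘out of sample’ on the remaining 20% of specimens in the same retrospective dataset". The first technique listed there for assessing and refining the model is called counterfactual analysis: "Input variables will be sequentially removed from and returned to the model to ascertain their likely causative impact". By the same sentence, that result settles which inputs the final model keeps. A separate item in the same list says that "measures such as log loss score and AUC-ROC will provide measures of model accuracy". Section 3.3.1 then evaluates the testing framework on the same 20% of specimens.

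Three other places bear on how this should be read:

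- Section 2, project question 1: "Can causal, explainable BCI approaches be used to develop/(re)validate (train/test) clinical prediction models".
- Section 1.2, on earlier studies with little specialist clinical input: they "suffer from an inability to separate causation from prediction", which the protocol treats as a key distinction in medical microbiology.
- Section 3.1.2, on candidate inputs: "Data on non-antimicrobial drugs will also be collected as this may be a surrogate marker of contact with healthcare". The same section gives previous antimicrobial exposure as a key route to resistance, and previous colonisation with a resistant organism as a risk factor for later resistant infection.

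**The concern.** Removing an input and refitting answers a conditional predictive question: how much worse are the predictions without this input, given all the others? A counterfactual question is different: how would the probability of resistance change if the input were set to another value? In observational data the two agree only under assumptions about confounding and mediation, and the removal step neither states nor tests them.

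The protocol fixes the procedure, its causal reading and the inclusion rule together, so this is not a detail left for later. It also repeats the confusion for which section 1.2 faults earlier work. At stake is what may be concluded for question 1. A causal label resting on this step would be unsupported, and a real cause could be marked as having little impact.

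A second issue follows from where the step is placed. If inputs are chosen by what happens on the 20% specimens, those specimens are no longer untouched when model performance and then the simulated evaluation are reported on them.

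**Working it through.** The protocol gives no figure on this point, so there is none to reproduce. The check has three parts.

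**1. Do the protocol's own inputs create the problem?** Yes, in both directions.

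- Credit to a non-cause. Non-antimicrobial drugs are collected because they may mark healthcare contact. If contact drives resistance and is imperfectly measured, the marker predicts resistance without causing it.
- Lost credit for a cause. Prior antimicrobial exposure can act by selecting resistant organisms, and prior resistant isolates are also candidate inputs. With the isolates kept in the model, removing exposure shows only the part of its effect that does not pass through them.

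**2. Simulation of the principle.** The protocol supplies the size (at least 250,000 specimens), the split and the initial model (logistic regression). The test set is 0.20 × 250,000 = 50,000 and the training set 0.80 × 250,000 = 200,000. The simulation used ordinary maximum-likelihood logistic fits. All effect sizes below are assumptions.

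*Scenario A, surrogate.* Unmeasured contact U ~ N(0, 1); surrogate S = U + N(0, SD 0.5); independent true cause A ~ N(0, 1); logit P(resistant) = −1 + 1.0·U + 0.3·A. The causal effect of S is zero. The model is fitted on S and A.

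*Scenario B, mediation.* Cause C ~ N(0, 1); mediator M = C + N(0, SD 0.5); logit P(resistant) = −1 + 1.0·M. One unit of C moves M by 1, and so the log-odds by 1 × 1.0 = 1.0, all of it through M. The model is fitted on C and M.

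| Scenario | Input dropped | Fitted coefficient in full model | Rise in test log loss | Fall in test AUC |
|---|---|---|---|---|
| A | Surrogate, causal effect 0 | 0.775 | 0.0630 | 0.1539 |
| A | True cause, log-odds 0.3 | 0.284 | 0.0072 | 0.0113 |
| B | Cause acting wholly through M | −0.002 | 0.0000 | 0.0000 |
| B | Mediator M | 1.008 | 0.0204 | 0.0278 |

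In scenario A the non-cause scores 0.0630 / 0.0072 ≈ 8.8 times the true cause on log loss. In scenario B a cause with a large total effect scores zero.

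A separately built simulation (200,000 specimens, 40,000 held out) agrees in direction. Dropping a zero-effect surrogate raised log loss by 0.0164. Dropping an exposure that raises risk from 0.252 to 0.501, a difference of 0.249, wholly through a prior isolate raised it by 0.000001.

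With 40,000 to 50,000 test specimens sampling error is not the explanation, and more data would not cure it.

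**3. Which data does the step use?** Section 3.2.2 assigns assessment to the remaining 20% and then lists the techniques for assessing and refining the model, with the removal step first. Section 3.3.1 runs the evaluation on the same 20%. Taken together, input selection is placed on the evaluation data. The size of the resulting optimism was not calculated.

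**The case against.** The strongest reply is that little depends on the causal label. The model's output is a probability of susceptibility. The primary and secondary outcomes are counts of actionable results, days to such results, and cost. In the simulations, keeping the surrogate and dropping the fully mediated cause are both sensible choices for a prediction model. All of this stands: ablation is a legitimate check of predictive contribution, and what fails is its causal interpretation and use as a causal inclusion rule.

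A reader might infer more than the documents support:

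- *That the study will publish false causal drivers of resistance.* No outcome promises a list of causes or an exposure effect, and the protocol says only that the impact is likely to be causative.
- *That surrogates are certain to enter the model.* Section 3.1.2 says the drug data will be collected and may be surrogates, and Table 1 describes data to be assessed for inclusion.
- *That prior exposure would show no contribution.* That result needs complete mediation. With a direct effect as well, credit would be reduced rather than lost.
- *That the protocol sets a log-loss cut-off for the removal step.* It states none; log loss and AUC-ROC appear in a separate item as accuracy measures.

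It can also be said that the reference cited for the step was not available, that further techniques will be tried, and that a causal diagram could sit in a statistical analysis plan. Its absence here is therefore not the finding. But none of this changes what removing and returning an input estimates.

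The use of the 20% specimens is a distinct matter and should not be counted as added weight for the causal point. With about 50,000 specimens its effect may be small.

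**Conclusion.** The concern holds in a limited form. As written, the step in section 3.2.2 measures conditional predictive contribution and cannot establish causative impact, so it cannot support the causal part of project question 1. The inclusion rule also pulls against section 3.1.2: if inclusion truly followed causation, useful surrogate markers would be excluded.

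The predictive part of question 1, the susceptibility probabilities and the primary outcome do not depend on the causal reading. The simulated figures rest on assumed effect sizes, an unmeasured common cause in scenario A and full mediation in scenario B. They show that the ranking can be wrong, not by how much it would be wrong here.

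Placing input selection on the 20% specimens is a fair reading of sections 3.2.2 and 3.3.1 and is avoidable. Its optimism is unquantified.

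**What to change.** 1. In section 3.2.2, rename the step predictor ablation and describe its result as contribution to prediction given the other inputs.
2. Select inputs by cross-validated log loss within the 80% training set. Fix the model there and keep the 20% for final evaluation only.
3. Limit the conclusion for project question 1 to explainable prediction. If a causal statement is wanted, prespecify a separate analysis with a named exposure, a causal diagram and the adjustment set that follows from it.

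The first and third changes are wording, unless the optional causal analysis is added. The second is routine cross-validation work and needs no new data. The downside is a more modest claim.

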## **3.3 Development and Clinical Evaluation of ADAPT-AST in a simulated clinical setting**

### **3.3.1 AST Decision Making Algorithm Development**

The final stage of the project will be evaluating the potential clinical and resource impact of the testing framework on the same 20% of samples used in the testing dataset above. To do this, a clinically suitable AST decision making model first will need to be developed. Comparison of a range of algorithmic approaches is likely to be required, but the aim of the first decision model trialled will be to select 7 antimicrobials for testing (the number in the standard first-line panel currently tested under existing LCL SOPs). The antimicrobials that will be initially eligible for AST selection are those for which probability calculations will be outputted, listed above in Table 2.

The first prioritisation approach trialled will be to rank antimicrobial choices in descending order of susceptibility uncertainty except for cefpodoxime and cefoxitin, then to apply an algorithm in Figure 4 to ensure that a mixture of oral and intravenous agents is tested.

[figure not shown]

Figure 4: Algorithm used to select 7 antimicrobials from the sorted shortlist.

\*Amoxicillin, Amoxicillin-Clavulanate, Aztreonam, Cefalexin, Ceftazidime, Phenoxycephalothin, Piperacillin-tazobactam.

Cefpodoxime or cefoxitin are not used as treatments in the local area, but resistance to either antimicrobial indicates a high probability of resistance mechanisms which preclude use of some beta lactams (BL) and beta-lactam-beta-lactamase-inhibitor combinations (BL-BLIC)(57,58). Therefore, the algorithm will also be designed for cefpodoxime and cefoxitin to only be tested when their susceptibility is sufficiently uncertain (a defined classification threshold will be calculated for this) and there is a chance of the affected BLs / BL-BLICs, cefpodoxime and cefoxitin all being tested as part of the panel of 7.

No additional weighting, ranking or exclusion criteria will initially be applied, but depending on evaluation based on a priori microbiology / clinical / health economic knowledge, measures may need to be taken to further steward the AST choices. These may include exclusion of certain antimicrobial choices which are less practically useful for UTI but for which resistance uncertainty may be high (e.g., teicoplanin) or algorithmic prioritisation/exclusion/weighting measures for factors such as WHO

AWaRe class, nephrotoxicity and risk of *Clostridioides difficile* diarrhoea. Stakeholder consultation by questionnaire will help to inform these sections of the algorithm. Participants in this element of the study will be:

- General Practitioners
- Antimicrobial Pharmacists
- Medical Microbiologists
- Infectious Diseases Physicians
- Acute Medicine Physicians
- Accident and Emergency Physicians
- Bacteriology senior biomedical scientist

Invitations to participate will be disseminated by all-user trust email, with compensation offered for participant time (within sponsor allowances). Participation will be outside time dedicated for clinical care. Formal informed consent of participants will be sought in writing via email, with opportunities for participants to ask questions provided via email and Microsoft Teams. The participant consent form is enclosed in Appendix 1. Once consent has been obtained, participants will be provided with a questionnaire (enclosed in Appendix 2) asking them to rank pseudonymised antimicrobials by order of appropriateness based on several factors. These findings will be analysed by linear regression to output regression coefficients, which will be considered for incorporation into the selection algorithm.

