#### ADAPT-AST Protocol

	Pivmecillinam Trimethoprim	Temocillin Vancomycin		
--	-------------------------------	--------------------------	--	--

Table 2: The group of antimicrobials from which ADAPT-AST will select a panel of 7 to test on each urine specimen, stratified by WHO AWaRe category. Cefpodoxime and cefoxitin are also part of the classification, but they are used purely in the laboratory for resistance phenotype screening purposes in Liverpool so have been left out of category as screening antimicrobials here.

A range of different BCI techniques will need to be trialled and compared for this process using open-source R, Stan, and Python coding languages on the open-source R-studio and PyCharm proprietary integrated development software platforms. A range of different BCI techniques will need to be trialled and compared for this process. However, binary LR with Markov Chain Monte Carlo (MCMC) estimation of the posterior distribution is likely to be the most appropriate initial trial technique for this because:

- A predictive model incorporating multiple input variables needs to be developed
- A supervised BCI statistical technique can be used here because the labels of the input variables are known
- The output variable only has two possible outcomes: 'S' for susceptible and 'R' for resistant
- The output variable can be expressed as a probability of outcome 'S' or 'R'
- Parameters will need to be estimated by random sampling from a posterior probability distribution which is influenced by random variables and in which there is probabilistic dependence between samples(53,54)

Proposed models will be trained on data from a randomly selected 80% of eligible specimens from the retrospective data from between 17th May 2017 and the present. The models will be based on a consistent time frame prior to each urine specimen chosen. This is because firstly the influence of prior data on current antimicrobial susceptibility probability is likely to diminish with increasing time, and secondly it will avoid bias being introduced by more data being available for specimens at the end of the dataset(39). Different periods will be trialled for those which give the highest predictive value. Wherever possible, algorithms will be designed in a 'modular' way with intuitive exchangeable components. This will increase the potential scalability and reapplication of algorithms in other settings (e.g., LMICs) with minimal algorithm modification.

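### Model refinement and variable choice sit in the testing step, and the same 20% hold-out then serves for the ADAPT-AST versus SOP comparison, so the out-of-sample claim is not secured

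*Protocol*

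**What the plan says.** Section 3.2.1 (Model Training) states: "Proposed models will be trained on data from a randomly selected 80% of eligible specimens". It also says "A range of different BCI techniques will need to be trialled and compared for this process" and, on the look-back window, "Different periods will be trialled for those which give the highest predictive value". It does not name the data on which that predictive value is scored.

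Section 3.2.2 (Model Testing) assesses performance "on the remaining 20% of specimens in the same retrospective dataset" and calls this out of sample. Its next sentence opens with "The techniques used to assess and refine the initial LR-derived model" and introduces two items:

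- Input variables are removed and returned in turn, to judge their likely causal role and "determine whether they should be included in the final model".
- For logistic regression, "measures such as log loss score and AUC-ROC will provide measures of model accuracy".

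Section 3.3.1 describes the final stage as "evaluating the potential clinical and resource impact of the testing framework on the same 20% of samples used in the testing dataset above". The decision model is to be developed first. The section expects several algorithmic approaches to be compared and a classification threshold to be calculated for cefpodoxime and cefoxitin, and assigns no data to either. Section 5 ends the study with analysis of the final algorithm version, which implies more than one version.

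**The concern.** Coefficients are fitted on the 80%, so this is not a matter of training on the test set. The issue is selection. If the variables kept in the final model are chosen by how the model behaves on the 20%, performance reported on that 20% belongs to a model picked partly because it did well there. Log loss and AUC-ROC then tend to look too good, and they are the evidence for project question 1. The ADAPT-AST versus SOP comparison uses the same specimens. It inherits the problem only so far as the selection criterion tracks the count of 'should' results.

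Using one hold-out first for predictive testing and then for clinical evaluation is acceptable if everything is fixed beforehand. The difficulty here is that reuse is combined with refinement placed in the testing step.

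**Working it through.** **Which data each step uses**

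| Step | Section | Data named |
|---|---|---|
| Fitting | 3.2.1 | 80% |
| Comparing techniques and look-back periods | 3.2.1 | scoring data not named |
| Assessing performance | 3.2.2 | 20% |
| Refining, choosing variables | 3.2.2 | not named separately; the 20% is the only dataset in the section |
| Comparing decision algorithms, setting the threshold | 3.3.1 | not named |
| ADAPT-AST versus SOP | 3.3.1, 3.3.2 | the same 20% |

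No section describes cross-validation, a validation subset or a lock.

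**Inputs.** Section 3.1.3 estimates at least 250,000 specimens: 0.8 × 250,000 = 200,000 for training and 0.2 × 250,000 = 50,000 held out. The protocol gives no number of candidates, correlation between them, SD, resistance rate or tested count per agent. All of these are assumed below. There is no plan figure to reproduce.

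**Formula.** For the best of K candidates with equal true performance and pairwise correlation r, the expected optimism is E(max) × √(1 − r) × SE. E(max) of K independent standard normals is 1.163 (K = 5), 1.539 (K = 10) and 1.867 (K = 20).

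**AUC-ROC, chosen separately for each agent.** K = 10, true AUC 0.70, 10% resistant, Hanley-McNeil SE:

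| Results for the agent | SE | r = 0.9 | r = 0.8 | r = 0.5 |
|---|---|---|---|---|
| 50,000 | 0.0043 | 0.0021 | 0.0029 | 0.0047 |
| 5,000 | 0.0136 | 0.0066 | 0.0093 | 0.0147 |
| 1,000 | 0.0303 | 0.0148 | 0.0209 | 0.0330 |

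For example, 1.539 × √0.5 × 0.0303 = 0.0330. Section 3.3.4 says some agents were not tested, so counts below 50,000 are expected for some. A joint choice across agents gives less.

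**Primary outcome.** Multiply by rho, the correlation between the sampling error of the selection criterion and that of the 'should' count, and take SE = SD/√50,000 with SD of the per-specimen difference 1 to 2. For K = 10:

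- rho = 1, low end: 1.539 × √0.1 × 1/√50,000 = 0.0022
- rho = 1, high end: 1.539 × √0.5 × 2/√50,000 = 0.0097, and 0.0097/7 = 0.14% of a 7-result panel
- rho = 0.5: 0.0011 to 0.0049
- rho = 0.25: 0.0005 to 0.0024
- rho = 0: nil

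At rho = 1, K = 5 gives 0.0016 to 0.0074 and K = 20 gives 0.0026 to 0.0118. A simulation of 200,000 runs (K = 10, r = 0.8, rho = 0.5) gave 0.346 SE against 0.344 from the formula.

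**Error rate, worst case.** Suppose 10 candidates all truly equal the SOP and the best is picked on the outcome itself. The chance of a false significant result in favour of ADAPT-AST, nominally 2.5%, becomes 6.4% at r = 0.9, 14.5% at r = 0.5 and 22.3% at r = 0 (simulation, 200,000 draws).

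**The case against.** The strongest reply is that section 3.2.2 never says variable removal is scored on the 20%. Only its first sentence names data, and removal could be done inside the 80%. Its stated purpose is causal impact. Log loss and AUC-ROC appear in a separate item as accuracy measures, so nothing says variables are kept for the best hold-out score. Technique and look-back comparisons sit under training, section 3.3.1 puts development of the decision model before evaluation, and an SAP, not available here, could fix the scoring data. Changes to the algorithm from prior knowledge or the questionnaire do not use the hold-out at all.

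Much of this stands. The reading is inferred, the look-back, threshold and decision-algorithm points are silence only, and bias on the primary outcome may be nil. The reply does not remove the core point: the protocol itself puts refinement in the testing step and fixes the same 20% for evaluation. An SAP that moved selection into the 80% would depart from the natural reading of the protocol.

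A second reply is that the effect is tiny. Models that differ by one variable and are scored on the same specimens may correlate above 0.9. At 0.99 with K = 10 the AUC optimism is about 0.0007 with 50,000 results and 0.005 with 1,000. That is fair. Section 3.3.4 also requires randomised studies before deployment, but those would test clinical impact and would not correct the predictive performance reported here.

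Third, the split is by specimen and some patients contribute several, so the two sets can share patients. That is a separate matter. The fix below does not address it and does not depend on it.

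**Conclusion.** The concern holds and should be fixed, with medium confidence because the use of the 20% for refinement is the natural reading and not an express statement. As written, the selected prediction model, and possibly the selected decision algorithm, is not assessed on data untouched by its selection.

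The expected distortion is small: a few thousandths of AUC for well-tested agents, up to about 0.03 for sparsely tested ones under the least favourable assumptions used here, and between nothing and about 0.010 results per specimen on the primary outcome. These ranges rest on 10 equally good candidates with correlation 0.5 to 0.9. The upper primary-outcome figure also needs selection on the 'should' count itself, which the protocol does not propose. The case for acting rests on the validity of the out-of-sample label for project question 1, not on a large bias.

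**What to change.** 1. In 3.2.2 and 3.3.1, state that variable selection, threshold setting and the choice between decision algorithms are done within the 80%, by cross-validation or a validation subset.
2. In 3.2.1, state that techniques and look-back periods are scored there too.
3. Lock the prediction model and decision algorithm, refit on the full 80%, and run that version once against the SOP on the untouched 20% as the primary comparison. Label results for other versions exploratory.
4. As a clarification only, say in 3.3.2 that the specimens on which both algorithms are run are those of the 20% test set, as 3.3.1 already implies.

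**Cost.** The wording is a few sentences; the computing depends on the route. Table 2 lists 10 + 10 + 3 + 2 = 25 agents.

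- Five-fold cross-validation: 25 × 5 = 125 MCMC fits per candidate instead of 25, plus 25 for the final refit. Removing each column once, with the 80 to 100 columns in Appendix 3 as a rough upper guide, means 10,000 to 12,500 fits instead of 2,000 to 2,500. Section 3.1.3 already names computing power as a constraint.
- 60/20/20 split: 25 fits per candidate plus 25 for the refit. The price is that candidates are compared on about 150,000 training specimens instead of 200,000. This is the cheaper route.
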